## Abbreviations

ALS	Amyotrophic Lateral Sclerosis
ALS-FRS	ALS Functional Rating Scale
APST	Ambulanzpartner Soziotechnologie
DSGVO	Datenschutzgrundverordnung (engl.: General data protection regulation)
fALS	Familial Amyotrophic Lateral Sclerosis
FTD	Frontotemporal Dementia
GDPR	General Data Protection Regulation
GenDG	Genetic Diagnostics Act (Gendiagnostikgesetz)
IEC	Independent Ethics Committee
MYMOP	Measure your Medical Outcome Profile
ODP	Order Data Processing
PEG	Percutaneous endoscopic gastrostomy
PI	Principal Investigator
sALS	Sporadic Amyotrophic Lateral Sclerosis
SMD	Standard Mean Difference

## Study Synopsis

Tracking Number:

Protocol Title: Clinical characteristics, natural history, health care measures, and the frequency of genetic variants in the genes of SOD1, C9orf72, FUS and TARDBP in patients with sporadic and familial amyotrophic lateral sclerosis (ALS)

Version Number: 2.6

Study indication: Amyotrophic Lateral Sclerosis (ALS)

Study rationale: There is only limited data available on the frequency of genetic variants in patients with sporadic ALS (sALS) and familial ALS (fALS). In patients with sALS (patients without family history of ALS), genetic investigations do not belong to the standard of care. As a result, the patient's mutation status is commonly unknown. Even in patients with fALS (with known family history of ALS), screening for genetic mutations is not performed on a regular basis, due to lacking treatment options in the field of gene therapy. However, this paradigm is about to be changing as clinical trials on genetic medicines are ongoing and might result in the approval of new genetically investigated drugs in the future. This project is intended to investigate a large cohort of ALS patients on family history, clinical characteristics, health care measures and genetic variants in SOD1, C9orf72, FUS and TARDBP – the most commonly mutated genes in ALS. This cohort study will allow to determine the frequency of gene mutations in ALS patients in a real-world setting of ALS centers in Germany. Furthermore, the project shall enhance insights into potential differences between genetically defined cohorts by means of the course of disease and the provision of health care measures. The investigation of genetically distinct ALS cohorts is particularly relevant, as an improved understanding of the relationship between the genotype and the journey of disease is scientifically indispensable, in order to determine the therapeutic potential of future genetic therapies.

Objectives and Endpoints: Primary objective

- To identify the frequency of genetic variants in the genes of SOD1, C9orf72, FUS and TARDBP in patients with sALS and fALS

Secondary objectives

- To investigate the demographic and social characteristics
- To investigate the family history for ALS or FTD
- To investigate the clinical classification, functional deficits and progression

- To register interventions and health care measures including percutaneous endoscopic gastrostomy (PEG), ventilation therapy,
- To register the provision with assistive technology devices, symptomatic pharmacotherapy and physical, occupational and speech therapy
- To investigate the clinical classification, functional deficits, disease progression and health care measures in a subset of ALS patients with pathogenic variants in the genes of SOD1 or C9orf72 as compared to ALS patients with no ALS-associated mutations in the investigated genes
- To register the values of serum concentration of neurofilament light chain (sNfL)
- To identify patient's treatment expectations towards ALS therapy using the Measure Your Medical Outcome Profile (MYMOP2)

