## 2. Introduction

### 2.1. Background

ALS is an adult-onset degenerative motor neuron disorder leading to progressive motor deficits and eventually to death within a few years (Brown et al. 2017). Currently, there is no effective disease modifying drug available. A distinction is made between sporadic and familial ALS (Kiernan et al. 2021). Sporadic ALS (sALS) refers to the occurrence of ALS in a single individual without known family history of ALS or frontotemporal dementia (FTD). Reportedly, population genetic studies in ALS found sALS in more than 90% of all ALS patients (Brenner et al. 2019, Kim et al. 2020, Volk et al. 2017, Zou et al. 2017). The term "familial ALS" (fALS) relates to the occurrence of ALS or FTD in several family members of a given trait. The definition of fALS encompasses positive cases of FTD as this neurodegenerative disorder may share common pathogenic pathways with ALS.

In patients with sALS, genetic tests for SOD1, C9orf72, TARDBP or other genes are not subject to standard care. The previous findings on the frequency of genetic variants in ALS-associated genes can be traced back to a few populations genetic studies of ALS (Volk et al., 2018). As a result, sALS patients and treating neurologists are commonly unaware of the patient's mutation status. Even in patients with positive or uncertain family history of ALS or FTD, screening for genetic mutations is not performed on a regular basis. Reportedly, ALS-associated genetic variants are mostly found in the genes of SOD1, C9orf72, FUS, and TARDP (Brenner et al. 2019, Kim et al. 2020, Volk et al. 2017, Zou et al. 2017). More specifically, mutations in SOD1 were found in 14.8% of patients with fALS and 1.2% of the sALS population. The disease is causing repeat expansions of the C9orf72 gene, among which 6.5% are identified of the total ALS cohort (34% of fALS, 5% of sALS) (Zou et al. 2017).

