## **3. Objectives and endpoints**

### **3.1. Objectives**

#### **3.2. Primary objective**

- To identify the frequency of genetic variants in the genes of SOD1, C9orf72, FUS and TARDBP in patients with sALS and fALS

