Patients who refuse to be notified about study results will not be informed about the outcome of genetic analysis. This patient's directive explicitly includes pathogenic mutations that might be of diagnostic or therapeutic relevance. The patient's directive of notification of all genetic study results will include normal findings (no or benign variants) genetic, genetic variants of unknown significance and pathogenetic mutations (likely pathogenic or pathogenic genetic variants in the investigated genes of SOD1, C9orf72, FUS and TARDBP. Results of diagnostic relevance are defined as genetic variants being known to cause ALS or can increase the risk of ALS or can modify the phenotype of the disease including the progression rate. The finding of pathogenic variants can lead to the diagnosis of fALS although the disorder – given the negative family history of ALS – has prior been classified as sALS. The diagnostic relevance can extend to other family members as likely pathogenic or pathogenic mutations in the study at ALS genes might substantiate a genetic risk for ALS to first- and second-degree relatives of study participants. Therapeutic relevance is defined by the planning or performance of a phase 3 clinical trial, a planned or ongoing early access program or an expected approval of genetic medicine targeting one of the studied genes within the next 12 months. Currently, therapeutic relevance can be stated for mutations found in the SOD1 gene. Therapeutic relevance of C9orf72 and FUS can be expected within the next few years post-approval of this study protocol. The definition of diagnostic and therapeutic relevance and the scheme of notification of individual study results is provided in table 11.

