### 12.3.3. Informed consent procedures of first and second-degree relatives

Study results on genetic variants of SOD1, C9orf72, FUS and TARDBP genes might be of diagnostic and therapeutic relevance of study participant's first and second-degree relatives. Relatives may include individuals with symptoms of ALS or FTD (established or probable diagnosis of fALS) as well as asymptomatic individuals (unknown risk of ALS). In principle, study participants are offered to provide the genetic study results to authorized family members. However, the knowledge and awareness about genetic research of study participants might be perceived as psychologically burdensome for first and second-degree relatives. The information includes the advice of genetic counseling prior to the notification of genetic study results. The study information and the offered genetic counselling will address the potential medical, psychological and social burden that can be associated with pathogenic gene mutations as well as the individual or societal benefits aimed with the study. Therefore, the provision of the study participant's genetic study results will be restricted and must comply with the following requirements:

- Authority for provision of study results to first and second-degree relatives by the study participant in a written manner
- Written information to first or second-degree relatives on the option of receiving genetic results of study participant
- Genetic counseling of first or second-degree relatives prior to signing informed consent on receiving genetic results of study participant
- Informed consent of first or second-degree relatives for receiving the study participant's genetic study results
- Directives of first or second-degree relative about the notification criteria of study participant's genetic results

The relative's directives concerning the notification criteria is part of the informed consent procedure. The notification criteria for relatives are the same as for the patient (see Table 12). The study results might be provided to authorized first and second-degree relatives after the death of the study participant (postmortem provision of participant's genetic study results).

*Table 12: Differentiated provision of genetic study results to first and second-degree relatives and modes of notification*

Patient's directive	Notification	Provision of study results
no notification	not applicable	not applicable

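### Does the synopsis wording on family history leave the sporadic and familial groups of the primary objective undefined?

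*Combined protocol and SAP*

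**What the plan says.** Section 3.2, repeated in the Study Synopsis, sets the primary objective: "To identify the frequency of genetic variants in the genes of SOD1, C9orf72, FUS and TARDBP in patients with sALS and fALS". Two descriptions of the groups appear.

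- **ALS only.** The rationale in the Study Synopsis has "In patients with sALS (patients without family history of ALS" and "Even in patients with fALS (with known family history of ALS". Section 12.3.1, explaining that a pathogenic finding may alter a diagnosis, speaks of patients earlier classed as sporadic "given the negative family history of ALS".
- **ALS or FTD.** Section 2.1 describes sporadic disease as arising "in a single individual without known family history of ALS or frontotemporal dementia (FTD" and adds: "The definition of fALS encompasses positive cases of FTD". Section 12.3.3 agrees: "Relatives may include individuals with symptoms of ALS or FTD (established or probable diagnosis of fALS".

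Table 5 counts first- and second-degree relatives with ALS and, separately, with FTD, living or deceased, at four levels of certainty. Table 1 places this at V1. Section 9.4 gives no rule that converts the counts into a group. Section 11 names neither group and provides only in general terms for subgroups on genetic, clinical or other baseline features.

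**The concern.** A frequency needs a defined denominator, whether or not a hypothesis is tested. A patient with an FTD-only family history is sporadic under the synopsis wording and familial under 2.1. Two analysts with the same Table 5 data could therefore report different primary results.

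The familial group is likely to be small, since 2.1 reports that studies "found sALS in more than 90% of all ALS patients", so moving a few patients could shift its percentages visibly. The protocol also says that familial disease may be undercounted, which makes the split part of the question.

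The remark in 12.3.1 adds a further worry. If a genetic result could move a patient from sporadic to familial, the group would depend on the endpoint it is meant to stratify.

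**Working it through.** **1. Which passage defines the groups?** The synopsis words stand in brackets inside a sentence about why testing is not routine. Section 2.2 repeats that rationale with no bracket. The matching sentence in 2.1 refers to a positive or uncertain history of ALS or FTD. The synopsis itself lists family history for ALS or FTD among its objectives and endpoints. Only 2.1 is written as a definition, and 9.4, Table 5 and 12.3.3 fit it. The ALS-only phrase in 12.3.1 is an aside in a section about notifying results.

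**2. How much does 2.1 settle?** As I read it, most of the rule.

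- *Number of relatives.* 2.1 gives no number for familial disease, but it requires no known family history for sporadic disease. One known affected relative already takes a patient out of the sporadic group.
- *Unknown history.* The condition is a known history, so an unknown one leaves the patient sporadic.
- *Degree.* Table 5 records first- and second-degree relatives only.
- *Certainty.* This stays open: nothing says whether a suspected case counts. Results can be tabulated by level.

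**3. Could the genetic result move a patient between groups in the analysis?** 12.3.1 concerns diagnosis and gives no instruction to restratify. 12.3.2 and Table 11 use the family-history label before testing. Section 2.1 quotes mutation rates in sALS (SOD1 1.2%, C9orf72 5%), which presupposes that carriers stay in that group. If every carrier of a pathogenic variant were relabelled, the sporadic frequency would be zero by construction and that half of the objective would be empty.

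**4. Can a size be given?** The plan has no figure to reproduce. The missing input is the share of patients with an FTD-only history. The figures below use C9orf72 only and are illustrative.

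Inputs from 2.1 and 5.1: 6.5% overall, 34% in fALS, 5% in sALS, N = 2,000.

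Implied familial share: (6.5 − 5)/(34 − 5) = 5.2%, so F = 103 and S = 1,897. The reference list gives the source as a meta-analysis, so these pooled rates need not share one mix. I therefore also use 10% (F = 200, S = 1,800), the bound implied by a sporadic share above 90%.

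Assumed: m = 20 or 60 FTD-only patients (1% or 3%), with carrier rate q = 5% or 34%.

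- Case A, the cited rates hold under ALS or FTD and the ALS-only rule is applied: fALS = (0.34F − qm)/(F − m); sALS = (0.05S + qm)/(S + m).
- Case B, the cited rates hold under ALS only and the 2.1 rule is applied: fALS = (0.34F + qm)/(F + m); sALS = (0.05S − qm)/(S − m).

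| F | m | q | A: fALS % | A: sALS % | B: fALS % | B: sALS % |
|---|---|---|---|---|---|---|
| 103 | 20 | 5% | 41.0 | 5.00 | 29.3 | 5.00 |
| 103 | 20 | 34% | 34.0 | 5.30 | 34.0 | 4.69 |
| 103 | 60 | 5% | 74.0 | 5.00 | 23.4 | 5.00 |
| 103 | 60 | 34% | 34.0 | 5.89 | 34.0 | 4.05 |
| 200 | 20 | 5% | 37.2 | 5.00 | 31.4 | 5.00 |
| 200 | 20 | 34% | 34.0 | 5.32 | 34.0 | 4.67 |
| 200 | 60 | 5% | 46.4 | 5.00 | 27.3 | 5.00 |
| 200 | 60 | 34% | 34.0 | 5.94 | 34.0 | 4.00 |

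For scale, the 95% half-width, 1.96 × √(p(1 − p)/n), is 9.1 points for 34% at n = 103, 6.6 points at n = 200, and about 1.0 point for 5% in the sporadic group.

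The familial figure moves by 0 to 40 points, depending only on m and q. The 74% needs 60 of 103 familial patients (58%) to qualify through FTD alone, and to carry no more often than sporadic patients. That sits badly with the shared disease pathways 2.1 gives as its reason for counting FTD. No sporadic shift exceeds its half-width, and that group is where the protocol says knowledge is weakest. The frequency in all patients does not move: (0.34 × 103.4 + 0.05 × 1,896.6)/2,000 = 6.5% under either rule.

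**The case for a change.** The best case for a change is this. Section 2.1 is background text, and nothing names it as the analysis definition. The ALS-only phrase occurs in two sections. Even if 2.1 governs, the certainty level is unset and the number of affected relatives has to be inferred. A rule chosen after the data are seen is open to doubt, and with 60 patients moved at the low carrier rate the familial shift exceeds sampling error in both cases. The repair would cost a few sentences.

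Part of this stands. The wordings do differ, and no derivation rule is written down. But a reader looking for a definition finds just one, and the data collection is built to match it. The large shifts come from inputs that the documents do not contain. The open choice of certainty level would remain the sponsor's even after the text was aligned. The evaluation is declared exploratory with no formal hypothesis, so no error rate hangs on the choice. Because Table 5 keeps ALS and FTD apart, whichever rule is used can be stated with the results and the other shown beside it.

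**Conclusion.** No change to the plan is needed. The synopsis phrase and its echo in 12.3.1 are loose wording, and the missing conversion of Table 5 into groups is a detail that analysts can fill sensibly from 2.1: family history of ALS or FTD at V1, taken independently of the participant's own genetic result. No data are lost under either rule, and the frequency in the whole cohort is unaffected.

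The documents support no size for the effect on the two groups, because they give no FTD-only share. The conclusion rests on reading 2.1 as the governing definition and 12.3.1 as a remark about diagnosis. It would weaken if the sponsor meant the ALS-only wording to govern, but Table 5 would still allow both sets of results.

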## **Endpoints**

### Primary endpoint

- Genetic variants in the genes of SOD1, C9orf72, FUS and TARDBP

### Additional endpoints

- The following additional endpoints will be explored:

#### *Family history of ALS and FTD*

- Family members living with ALS or FTD
- Family members who have died from ALS or FTD

#### *Clinical classification, functional deficits and progression*

- ALS subtypes (classic ALS, progressive muscular atrophy (PMA) and primary lateral sclerosis (PLS))
- Topic of the initial symptoms
- ALS Functional Rating Scale (ALS-FRS)
- ALS progression (ALS-FRS per months)
- King's classification of clinical stages of ALS
- Serum neurofilament light chain (sNfL)

#### *Interventions and health care measures*

- Percutaneous endoscopic gastrostomy (PEG)
- Non-invasive ventilation
- Tracheostomy
- Provision with assistive technology devices
- Symptomatic pharmacotherapy
- Physical, occupational and speech therapy

#### *Patient's expectations towards ALS therapy*

- Measure Your Medical Outcome Profile (MYMOP2)

	This evaluation is exploratory. There is no formal hypothesis that is tested.
Study design:	This study is a prospective, non-interventional registry study (analytical observational study) in an inter-cohort comparison at 18 study centers in Germany.
Study location:	18 study sites in Germany
Number of subjects:	Approximately 2,000 subjects
Study period:	The study period is about two years (August 2021 until December 2024)
Study population:	This study will be conducted in subjects aged at least 18 years, inclusive, with a diagnosis of sporadic or familial ALS.
Assessment Schedule	Study subjects will have up to 3 assessments over a period of approximately 1 year.
Key study assessments:	
Genetic variants in four ALS-associated genes
 
 
• SOD1 gene
 
• C9orf72 gene
 
• FUS gene
 
• TARDBP gene
 
 
Family history for ALS or FTD
 
 
• Family members living with ALS or FTD
 
• Family members who have died from ALS or FTD
 
 
Clinical classification, functional deficits, and progression
 
 
• ALS subtypes (classic ALS, progressive muscular atrophy (PMA) and primary lateral sclerosis (PLS))
 
• Topic of the initial symptoms
 
• ALS Functional Rating Scale (ALS-FRS)
 
• ALS progression (ALS-FRS per months)
 
• King's classification of clinical stages of ALS
 
• Serum neurofilament light chain (sNfL)
 
 
Interventions and health care measures
 
 
• Percutaneous endoscopic gastrostomy (PEG)
 
• Non-invasive ventilation
 
• Tracheostomy
 
• Provision with assistive technology devices
 
• Symptomatic pharmacotherapy
 
• Physical, occupational and speech therapy
 
 
Patient's expectations towards ALS therapy
 
 
• Measure Your Medical Outcome Profile (MYMOP2)
 

Statistical methods:	The standardized mean difference (SMD) will be applied in this study. The SMD of each measure over up to 12 months will be estimated using the change in measure between each subject's assessments. The standardized mean difference expresses the size of intervention effect.
Sample size determination:	Due to this partly exploratory background of study project, a sample size justification is not applicable. The sample size is based on the feasibility of eligible patients to be enrolled at this site and is not based on power calculation.
Interim analysis:	An interim analysis may be performed.
Study stopping rules:	Not applicable for an observational study.

## 1. Visit schedule

Table 1: Visit schedule

Visit schedule	V1 M1-M3 (Baseline)	V2 M4-M8* (Follow-Up)	V3 M9-M14 (Closure)
Demographic data			
Age	x		
Gender	x		
Place of residence	x		
Social characteristics			
Employment status	x		
Marital status	x		
Education level	x		
Living arrangement	x		
Disease history			
Date of disease onset	x		
Date of initial diagnosis	x		
Age at disease onset	x		
Duration of disease	x		
Date of death (if applicable)			
Family history			
Family members who are living with ALS	x		
Family members who died of ALS	x		
Family members who are living with FTD	x		
Family members who died of FTD	x		
Family members who are suffering from neurological/psychiatric disorder	x		
Family members who died of any neurological/psychiatric disorder	x		
Clinical classification			
ALS subtypes	x		
Region of onset	x		
Functional deficits and progression			
ALS Functional Rating Scale (ALS-FRS)	x	x(2)	x
ALS progression rate (loss of ALS-FRS per month)	x	x(2)	x
King's classification of clinical stages of ALS	x		x
Serum neurofilament light chain (sNFL)	x	x(2)	X(2)
Interventions and health care measures			
Use of PEG	x		x
Use of non-invasive ventilation	x		x

Use of tracheotomy	x		x
Provision of a manual wheelchair (1)	x		
Provision of complex power wheelchair (1)	x		
Provision of a communication device (1)	x		
Provision of assistive technology (1)	x		
Physical, occupational and speech therapy (1)	x		
Riluzol and symptomatic pharmacotherapy (1)	x		
Treatment expectation			
MYMOP2, measure yourself outcome profile	x	x(2)	x(2)
Molecular genetic analysis			
C9orf72	x		
FUS	x		
SOD1	x		
TARDP	x		

M: month, V: visit; 1 = subgroup of users of APST management platform, 2 = in subgroup of patients with SOD1 mutation data will be collected more frequently (up to monthly collection of existing data of sNfL; up to weekly self-assessment of ALS-FRS using the ALS-App in addition to on-site assessment of ALSFRS-R during site visits). In the main cohort of non-SOD1 patients the collection of sNfL data is limited to the visits V1 (baseline) and V2 (follow-up).

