## **4. Overall study design**

### **4.1. Study design**

This is a longitudinal, non-interventional, non-randomized, multicenter, prospective study conducted in subjects with ALS. Duration of study participation for each subject will be up to approximately 12 months. Subjects will be enrolled to receive questionnaires, in order to assess the variables and to provide blood samples for molecular genetic testing. Approximately 1,000 subjects are planned to complete the study. It is anticipated that up to approximately 18 sites will be activated in Germany. This registry study will be reported according to STRO-BE-statement.

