## **5. Study subjects**

### **5.1. Number of study subjects**

2,000 subjects are planned to be recruited. More than 1000 subjects are expected to complete the end-of-study assessments, after an observation period of 12 months.

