## 9.7. Interventions and health care measures

Data on clinical interventions and health care measures will be collected as follows:

*Table 8: Items used to describe clinical interventions and health care measures*

Item	Description
Percutaneous endoscopic gastrostomy (PEG)	Y/N Date of provision (MM/YYYY)
Non-invasive ventilation (NIV)	Y/N Date of provision (MM/YYYY) Usage up to 8 hours per day Usage 8 to 16 hours per day Usage more than 16 hours per day
Invasive ventilation (IV)	Y/N Date of provision (MM/YYYY)
Provision of manual wheelchair (1)	Y/N Date of provision (MM/YYYY)
Provision of complex power wheelchair (1)	Y/N Date of provision (MM/YYYY)
Provision of augmented communication device (1)	Y/N Date of provision (MM/YYYY)
Provision of assistive technology (e. g. robotic arms), (1)	Y/N Date of provision (MM/YYYY)
Physical therapy (2)	Y/N Treatment units per week
Occupational therapy (2)	Y/N Treatment units per week
Speech and swallowing therapy (2)	Y/N Treatment units per week
Pharmacological therapy (3)	Riluzol, Y/N Symptomatic drugs, number of medicines

(1) Data will be obtained in a multi-center subset of up to 300 participants

(2) Data will be obtained in a single-center subset of up to 100 participants

(3) Data will be obtained in a multi-center subset of up to 200 participants

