cases, since not all patients are expected to complete end-of-study assessments due to disease progression, e.g., death. It is aimed to compare the baseline characteristics and the proportion of death between those who completed and not those not completed 6 months and 12-month assessment. Statistical significance will be ascertained by according to an error risk of up to 5% (p-value < 0.05). Associations for the clinical outcomes will be assessed by linear regression models adjusted for potential confounding factors. Results of the longitudinal observations will be also controlled for the influence of any covariate (sex, age, intervention history). Longitudinal analysis by means of group comparisons will be applied by using a multivariate analysis. 95% confidence intervals with p-values will be reported. In order to draw conclusions from the samples with censored data, missing data records will be omitted and treated as missing values. Data analysis will be performed using SPSS (Version 25.0).

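### PEG, non-invasive ventilation and tracheotomy have no scheduled, dated capture between V1 and V3 and no record check for patients who miss V3, so starts after baseline may be missed selectively

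*Combined protocol and SAP*

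**What the plan says.** Table 1 in section 1 has rows for PEG, "Use of non-invasive ventilation" and "Use of tracheotomy". Each is marked at V1 (months 1 to 3) and at the last visit, "V3 M9-M14 (Closure"). Each is blank at V2 (months 4 to 8), although V2 is planned for all subjects (section 4.3) and ALS-FRS is marked there.

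Table 8 in section 9.7 asks, for PEG, non-invasive ventilation and invasive ventilation, for yes/no and "Date of provision (MM/YYYY"). Sections 8.1 and 8.2 name medical records as a source for interventions and allow some data to be collected retrospectively. They set no time or trigger for doing so after baseline. Section 7 asks only for the reason when a patient is withdrawn.

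On numbers, section 5.1 says "2,000 subjects are planned to be recruited" and "More than 1000 subjects are expected to complete the end-of-study assessments, after an observation period of 12 months". Section 4.1 says "Approximately 1,000 subjects are planned to complete the study".

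Section 11 limits the follow-up analysis to complete "cases, since not all patients are expected to complete end-of-study assessments due to disease progression, e.g., death". Section 3.3 makes the comparison of health care measures between SOD1 or C9orf72 carriers and mutation-negative patients an objective, and section 11 extends the group comparisons to changes over time.

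**The concern.** A date of provision entered at V3 recovers an earlier start only in a patient who attends V3. Take a patient who attends V2, then receives ventilation or a PEG, and dies before V3. Nothing in the schedule prompts anyone to record either event. The same applies to a patient already ventilated at V2 who does not reach V3.

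These losses are unlikely to be random. The plan itself attributes non-completion to disease progression, and the three items respond to nutritional and respiratory failure. Two results are at stake: the estimate of uptake during follow-up, and the genotype comparison of these measures if the groups lose different shares of patients before V3. Section 11's planned comparison of completers with non-completers would not reveal the problem, because it covers baseline characteristics and deaths, not interventions.

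**Working it through.** **Inputs from the documents.** Recruited: N = 2,000 (section 5.1). Completers: c is about 1,000 (section 4.1) or more than 1,000 (section 5.1). V2 window: months 4 to 8 (Table 1). The documents give no dropout or mortality rate, so the completer figure cannot be reproduced independently. It can only be converted to a loss.

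**Patients without V3.** Share = (N − c)/N.
- c = 1,000: 1,000/2,000 = 50%
- c = 1,200 (assumed): 800/2,000 = 40%
- c = 1,400 (assumed): 600/2,000 = 30%

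Half is the central value under section 4.1 and the upper limit under section 5.1.

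**Patients seen at V2 but not at V3.** Assume a constant loss rate over 12 months. The number still followed at month m is N × (c/N)^(m/12). Subtract c.

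| V2 at month | c = 1,000 | c = 1,400 |
|---|---|---|
| 4 | 1,587 − 1,000 = 587 | 1,776 − 1,400 = 376 |
| 6 | 1,414 − 1,000 = 414 | 1,673 − 1,400 = 273 |
| 8 | 1,260 − 1,000 = 260 | 1,577 − 1,400 = 177 |

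These are the patients for whom a mark at V2 would add a dated status.

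**Share of post-baseline starts that fall in patients without V3.** With start risks p_n in non-completers and p_c in completers, the share is (N − c)p_n / [(N − c)p_n + c·p_c]. The risks are assumptions.
- Equal risks (0.2 and 0.2): 200/400 = 50% for c = 1,000; 120/400 = 30% for c = 1,400
- Double risk in non-completers (0.4 and 0.2): 400/600 = 67% for c = 1,000; 240/520 = 46% for c = 1,400

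**Effect on reported uptake.** A complete-case analysis reports uptake in completers only. With assumed 12-month uptake of 15% in completers and 30% in non-completers:
- c = 1,000: true uptake 0.5 × 15% + 0.5 × 30% = 22.5%, reported 15%
- c = 1,400: true uptake 0.7 × 15% + 0.3 × 30% = 19.5%, reported 15%

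If the two rates are reversed, with c = 1,000, true uptake is again 22.5% but 30% is reported. If they are equal there is no bias. The sign therefore depends on a difference that the documents do not give.

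**The case against.** The strongest reply is that a blank cell does not prove that nothing is collected. Medical records are a named source, a date field exists, and date of death is to be collected (section 9.3) although its row in Table 1 has no mark at any visit. A site could look up the chart before the database is closed. This stands, and it defeats two readings that a reader might infer: that these interventions are never captured in non-completers, and that the gap could not be repaired later. What remains is that no section requires the look-up, so capture depends on each site's habit.

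Second, ALS-FRS at V2 covers nutrition and ventilation (section 9.6.1) and is stored by item (Table 7). This also stands, but the signal is indirect and undated, and it is silent on starts after the last ALS-FRS assessment. SOD1 patients may self-rate up to weekly (Table 1, note 2), so using it as a substitute would make ascertainment unequal between the groups being compared.

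Third, not every non-completer could contribute. Section 7 lists withdrawal of consent as a reason for leaving, and section 12.7 provides for erasure of those data. A reader should not infer that all 1,000 are recoverable.

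Fourth, under a complete-case rule non-completers leave both numerator and denominator, so the direction of bias is not fixed. That is correct, as the reversed example shows.

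Finally, the primary endpoint is variant frequency, and these measures are additional, exploratory endpoints without a formal hypothesis. This limits the weight of the point but does not remove it, because the comparison is a stated objective.

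**Conclusion.** The point holds in this form: dated capture of the three items is scheduled only at V1 and V3, and no record check is specified for patients who miss V3. Starts after baseline may be missed in up to about half of the cohort: about 1,000 of 2,000 under section 4.1, and fewer under section 5.1 (600 if 1,400 complete, an assumption). Because loss is linked to progression and death and the follow-up analysis is complete-case, uptake during follow-up and the genotype comparison can be biased.

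Understated uptake is plausible if patients who progress and die receive these interventions more often. A reader might take that as established, or conclude that the genotype with more losses will appear to have less intervention. The documents give no uptake by completion status or by genotype, so they support neither the direction nor the size. The 260 to 587 patients seen at V2 but not V3 rest on constant loss to 1,000 completers. The change is worth making because it is cheap; the main result of the study does not depend on it.

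**What to change.** 1. In Table 1, mark PEG, non-invasive ventilation and tracheotomy at V2. Table 8 has an invasive ventilation row but none named tracheotomy, so state which field holds that item.
2. Add one entry at death, missed V3 or withdrawal, in which the site transfers yes/no and date of provision for the three items from the medical record, a source already allowed by sections 8.1 and 8.2. Exclude patients who withdraw consent, in line with section 12.7. Record date of death and last known date in the same entry.
3. In section 11, exempt these three items from the complete-case rule. Report them for all enrolled patients as time from baseline to first provision, censored at the last known date, with death as a competing event. Report patients who already have the item at V1 as prevalent at baseline. Without this step, a mark at V2 alone would change little, because non-completers would still be dropped.

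The cost is three extra items at an existing visit, one chart look-up per non-completer (up to about 1,000, less those who withdraw consent), and a time-to-event summary in the analysis. Patients undergo no new procedure.
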